#### 9.3 TRANSFER OF DATA

Data transfer from sites to TCTU and from TCTU and HIC to Sponsor Institution/co-investigators (e.g. HERA) will be via LabKey, a secure data transfer server facility provided by TCTU.

Data will be retained for at least 15 years. Archiving and destruction will be as per Sponsor SOP.

#### **10 SAFETY ASSESSMENTS**

As the study is defined as a non-Clinical Trial of Investigational Medicinal Product, Adverse Events (AE) and Serious Adverse Events (SAE) not defined on the exception list (see Section 10.1.1) will be recorded and reported as per Health Heath Research Authority (HRA) and Sponsor's guidelines for non-CTIMP reporting (summarised in Table 5**Error! Reference source not found.**).

A serious adverse event (SAE) is defined as an untoward occurrence that:

- (a) results in death;
- (b) is life-threatening;
- (c) requires hospitalisation or prolongation of existing hospitalisation;
- (d) results in persistent or significant disability or incapacity;
- (e) consists of a congenital anomaly or birth defect; or
- (f) is otherwise considered medically significant by the investigator.

Note: Hospitalisations for treatment planned prior to randomisation and hospitalisation for elective treatment of a pre-existing condition will not be considered as an SAE. However, any adverse events occurring during such hospitalisation will be recorded. See section 10.1.1 for further AE and SAE reporting exemptions.

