#### 2.2.2 Secondary Outcomes

- 1) Change in haemoglobin levels between baseline and 3 months
- 2) Change in ferritin levels between baseline and 3 months
- 3) Number of eligible patients per site
- 4) Proportion of eligible patients agreeing to take part and passing screening
- 5) Feasibility of collecting proposed outcomes at baseline and 3 months for a future definitive trial:
  - Short physical performance battery (15)
  - Six-minute walk distance
  - Anaemia-related symptoms (e.g. breathlessness, tiredness, fatigue)
  - Health-related quality of life (EQ-5D-5L™, 15D©) (16, 17) (20)

- Activities of daily living (NEADL©) (18)
- Health care use including use of blood transfusions and hospitalisation
- All-cause mortality
- 6) Dropout rate at 3 months
- 7) Crossover rate at 3 months
- Change in functional limitation (six-minute walk <400m or short physical performance battery score ≤10) scores between baseline and 3 months
- Change in level of fatigue assessed using validated Fatigue Severity Scale (19) between baseline and 3 months
- 10) Change in medication adherence using Oral Iron Use Likert scale (in those taking oral iron only) between baseline and 3 months
- 11) Participant experience using semi-qualitative questionnaire at 3 months.

[figure not shown]

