#### 4.2 INCLUSION CRITERIA

To be eligible, the participant will be assessed, and must meet all of the following criteria:

- 1. Provision of written informed consent
- 2. Community dwelling (i.e. not in hospital)
- 3. Age 65 years or over
- 4. Haemoglobin of >=85g/L and <=110g/L prior to commencing oral iron
- 5. Ferritin <100µg/L prior to commencing oral iron
- 6. Currently taking oral iron at any dose with a minimum of 8 weeks therapy
- Insufficient response to oral iron therapy (sufficient response defined as improvement in Hb of 20g/L after a minimum of 8 weeks of oral iron therapy or above lower limit of normal Hb level for sex)
- 8. Relevant investigations (including upper and lower GI endoscopies) either already conducted, offered but declined by the patient, or deemed not appropriate by the treating clinician. Only if applicable:
- 9. Oral iron therapy provided an initial sufficient response however Hb has now fallen below lower limit of normal for sex (Sufficient response is defined as an improvement in Hb of 20g/L or Hb above lower limit of normal for sex after a minimum of 8 weeks of oral iron therapy).

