## 10.1.1 AE & SAE Exception List

Due to the large amount of comorbid disease and very high levels of illness and adverse events that we expect to be present in this population, we will record all Adverse Events but not report to REC those classified as SAEs, in the following categories:

- Any death or hospitalisation due to a new cardiovascular event
- Any death or hospitalisation due to new diagnosis or treatment of cancer

- Any death or hospitalisation due to exacerbation of an existing medical condition
- Any admission for elective or planned investigation or treatment
- Any death or hospitalisation due to nausea, vomiting, constipation or diarrhoea
- Any death or hospitalisation due to a fall.

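### Sections 10 and 10.1.1 give a booked admission for anaemia that worsened on study two different statuses, non-SAE and recordable SAE

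*Protocol*

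**What the plan says.** Protocol section 10 makes an event serious if, among other criteria, it "requires hospitalisation or prolongation of existing hospitalisation" (criterion c) or "is otherwise considered medically significant by the investigator" (criterion f). A Note then takes two kinds of admission out of the definition. The first is "Hospitalisations for treatment planned prior to randomisation". The second is covered by the words "hospitalisation for elective treatment of a pre-existing condition will not be considered as an SAE". The Note adds one safeguard: "However, any adverse events occurring during such hospitalisation will be recorded".

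Section 10.1.1 is an exception list. Its opening sentence says that all adverse events are recorded, and that SAEs in the listed categories are not sent to the ethics committee. One category is "Any admission for elective or planned investigation or treatment". Another is death or admission caused by worsening of an illness the participant already had.

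Section 4.2 admits people with iron deficiency anaemia and "Insufficient response to oral iron therapy", or a relapse after an initial response. Section 5.5.1 randomises them to continue oral iron, stop it, or stop it and receive IV iron. Section 2.2.2 also collects "Health care use including use of blood transfusions and hospitalisation".

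**The concern.** The first limb of the Note is tied to randomisation; the second is not. Admissions already planned at randomisation fall under the first limb, so the second adds mainly admissions arranged afterwards. It also lacks the usual proviso that the condition has not worsened on study.

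That matters in this population. The condition under treatment is present in everyone at entry, one arm stops iron, and another continues a treatment to which the response was inadequate. Falling haemoglobin leading to a booked admission is a foreseeable bad outcome of a strategy, and it is also treatment of a pre-existing condition. The safeguard covers what happens during the admission, not the deterioration that caused it.

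There is a possible asymmetry between arms. An acute reaction to an infusion would lead to an unplanned admission, which remains an SAE. Failure of a strategy can lead to a planned one, which the Note removes. At stake is whether SAE counts by arm and by site mean the same thing when they inform the definitive trial.

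**Working it through.** No arithmetic applies: the protocol states no rate of such admissions and no SAE figure to reproduce. The check applies both sections to each kind of admission.

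| Admission | Section 10 definition and Note | Section 10.1.1 |
|---|---|---|
| A. Planned before randomisation | Not an SAE (first limb) | Elective or planned category: recorded, may be an SAE, not sent to the ethics committee |
| B. Booked after randomisation, existing condition unchanged | Not an SAE (second limb) | As A |
| C. Booked after randomisation, anaemia worsened on study | Not an SAE (second limb) | Elective category and worsened-illness category: recorded, may be an SAE, not sent to the ethics committee |
| D. Unplanned, anaemia worsened on study | SAE under criterion (c); the Note does not apply | Worsened-illness category: recorded SAE, not sent to the ethics committee |
| E. Day-case visit for infusion or transfusion | Not stated whether criterion (c) is met | Not stated |

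**Step 1.** Rows A to C carry a different status in each section. In A and B this is largely harmless, because such admissions need not reflect the allocated strategy.

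**Step 2.** Row C is where it matters. Rows C and D describe the same deterioration and differ only in whether a bed was booked. Section 10.1.1 puts both under worsened illness, with no limit to unplanned admissions. The Note separates them.

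**Step 3.** Could the sections be read in sequence, the Note first and the list only for what remains? Section 10 does refer to 10.1.1 for further exemptions. On that reading the contradiction goes, but every row C event falls outside the SAE definition unless criterion (f) is invoked. If instead 10.1.1 governs, row C is a recorded SAE. The text does not settle the order, so four sites could follow different readings.

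**Step 4.** What is still captured? Section 10.1 records adverse events that led the participant to seek professional advice or treatment, so the worsening is recordable. Section 7.2 has the hospital record reviewed at visit 4. The Care Use Questionnaire (Appendix 3) asks about hospital visits because of anaemia, nights stayed, infusions and transfusions. The event survives in the data; its serious status is what is uncertain. The questionnaire is self-reported from memory and assigns neither seriousness nor causality.

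**Step 5.** Section 2.2.1 defines the co-primary outcomes as randomisation rate and recruitment by route. Neither uses SAE data.

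**The case against.** The strongest reply is that 10.1.1 already answers the concern. An admission arranged because haemoglobin fell is naturally an admission for a worsened existing illness, and 10.1.1 treats that as a recorded event that may be an SAE. Criterion (c) keeps every unplanned admission and criterion (f) leaves the investigator free to call the deterioration serious. Section 9.2 costs IV iron as outpatient or day-case visits, which may not be hospitalisations at all. The safety outcomes named in section 9.2 are adverse event rates and falls, with no between-arm SAE test.

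Most of this stands, and it narrows the point. It does not remove it: 10.1.1 does not say that it overrides the Note, and discretion under (f) is no substitute for a consistent rule.

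A reader might infer three stronger things that the documents do not support:

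- **That planned admissions after a failed strategy are never SAEs.** This follows only if the Note is read alone or given priority. Section 10.1.1 points the other way.
- **That the exclusion could account for the whole SAE difference between arms.** No rate is given for these admissions or for other SAEs in any arm, and 10.1.1 itself anticipates a great deal of other illness.
- **That the annual safety report loses these events because of the Note.** The section 10.3 report covers causally related SAEs, section 10.1 ties relatedness to the research procedures, and 10.1.1 already withholds these categories from committee reporting. Changing the Note would not clearly restore them.

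**Conclusion.** The point holds as a conflict between two SAE rules. The open-ended limb in section 10 makes a booked admission after randomisation for worsened anaemia a non-SAE; section 10.1.1 treats the same admission as a recorded event that may be an SAE. Classification may then vary between sites, and SAEs may be undercounted in whichever arms the strategy fails.

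The size cannot be stated from the documents. It depends on how often such admissions occur, how many are booked rather than unplanned, how many involve more than a day-case visit, and how often criterion (f) is used. The direction of any undercount assumes that strategy failure differs by arm, which is plausible but not shown. The defect concerns safety classification in a pilot, and correction is worthwhile because the conflict touches a foreseeable harm and is cheap to remove.

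**What to change.** Reconcile the two sections.

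1. In the section 10 Note, limit the exclusion to admissions planned before randomisation, or elective admissions for a condition that has not worsened since randomisation. State that hospitalisation for anaemia that worsened on study is recorded as an SAE whether or not it was booked.
2. In section 10.1.1, word the elective-admission line so that it covers only admissions that remain SAEs under the amended Note. The exemption from ethics committee reporting can stay.
3. State whether a day-case visit counts as hospitalisation under criterion (c).

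This is a sentence or two in each section and changes recording only, not the care of any participant. The cost is a few more SAE entries, so the reported counts may look slightly less favourable.

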#### 10.1 RECORDING AND REPORTING AEs AND SAEs

AEs and SAEs will be recorded from the time of written informed consent until the last study visit.

- Only AEs which have resulted in the participant seeking advice or treatment from a healthcare professional will be recorded.
- The PI or delegate will ask about the occurrence of AEs and hospitalisations visits 2 and 4 only.
- Once the Investigator becomes aware that an AE or SAE has occurred in a study participant, they
  must enter the information into the CRF AE Log and entered (in a timely fashion) into the
  OpenClinica database.

• Participants with unresolved AEs at the last study visit will be followed up until resolution or 30 days after their last study visit, whichever is sooner.

An SAE occurring to a research participant will only be reported as per HRA guidelines to the main REC, and copied to the Sponsor (as per University of Aberdeen SOP) via [contact], where in the opinion of the Chief Investigator the event was:

Related - that is, it resulted from administration of any of the research procedures, and

*Unexpected* – that is, the type of event is not listed in the protocol or Reference Safety Information (section 6.3) as an expected occurrence.

unless meeting a AE/SAE reporting exception category, as outlined in section 10.1.1 (below).

	Who	When	How	To whom
SAE	Chief Investigator (CI)	Within 15 days of the	SAE report form for non-	Main REC for the
		CI becoming aware of	CTIMPs	study.
		the event		
Urgent safety	Chief Investigator (CI)	(i) Immediately	(i) By telephone	Main REC: study
measures	or sponsor	(ii) Within 3 days	(ii) Notice in writing setting	co-ordinator will
	Or exceptionally by		out the reasons for urgent	acknowledge
	local principal		safety measures and the	within 30 days
	investigator (PI)		plan for further action	

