#### S.2 SCIENTIFIC SUMMARY

Anaemia is a common problem, and is particularly common in older people. It is associated with fatigue, impaired functional capacity, increased hospitalization and mortality. In the USA, the prevalence of anaemia as defined by the World Health Organisation (Hb <130g/L in men and <120g/L in women) among community-dwelling adults age 65 years and older was 11.0% and 10.2% in men and women, respectively, rising to more than 20% in those >85 years.

In this pilot study we will recruit older people, aged 65 years or over, with mild-moderate iron deficiency anaemia (anaemia defined as haemoglobin (Hb) between 85 and 110 g/L and iron deficiency defined as ferritin <100µg/L prior to commencing oral iron) and who show insufficient response to oral iron therapy (sufficient response defined as improvement in Hb by 20g/L within 3 months of commencement of oral iron therapy) into a three-arm study. The study arms are:

- Treatment as usual
- Stop oral iron treatment
- Stop oral iron and give IV iron (as per local formulary).

The co-primary outcomes are:

- 1) the rate of randomisation per month across the pilot sites
- 2) the proportion recruited from each route of recruitment

Secondary outcomes are:

- 1) change in haemoglobin and ferritin levels at 3 months
- 2) number of eligible patients per site
- 3) proportion of eligible patients agreeing to take part and passing screening
- feasibility of collecting primary (physical functioning and health-related and general quality of life) and secondary outcomes for main trial:
  - Short physical performance battery
  - Six-minute walk distance
  - Anaemia-related symptoms (e.g. breathlessness, tiredness, fatigue)
  - Health-related quality of life (EQ-5D-5L™, 15D©)
  - Activities of daily living (NEADL©)
  - Health care use including use of blood transfusions and hospitalisation
  - All-cause mortality
- 5) dropout rate at 3 months; crossover rate at 3 months

- 6) reported side effects and adverse events (GI symptoms, headache, dizziness, rash)
- 7) functional limitation (six-minute walk <400m or short physical performance battery ≤10)
- 8) level of fatigue assessed using validated Fatigue Severity Scale
- 9) Patient experience.
- 10) Oral Iron Use Likert Scale (in those taking oral iron only)
- 11) Participant experience using semi-qualitative questionnaire.

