#### 1.2 RATIONALE FOR THE STUDY

A satisfactory response (rise in Hb of 20g/L) to oral iron is usually expected within 6-8 weeks of commencing treatment. The current standard of care is to continue oral iron even if a suboptimal (or no) response is seen. It is unclear if the current standard of care is of value to patients and healthcare providers. The balance of benefit and harm for oral iron in older people is unclear, and the best strategy for those not responding to oral iron is also unclear. Should oral iron be continued for longer, switched to intravenous iron, or simply stopped if it is not working? It is also uncertain whether further oral or IV iron therapy improves physical function and quality of life compared to no therapy in older patients with iron-deficiency anaemia.

We conducted an online survey of geriatricians and GPs in November 2016 through the British Geriatrics Society. Our survey confirmed the uncertainties in managing IDA, evident by inconsistent approaches and lack of clinicians' knowledge on whether the choice of management actually improved patient outcome. Over 85% of respondents stated that they regularly prescribe oral iron in at least 50% of their patients with IDA. 30% of respondents regularly prescribe oral iron in almost all of their patients with IDA. Although >85% who responded were willing to facilitate recruitment of eligible patients into a trial, they indicated some reluctance to discontinue oral iron therapy. Therefore, the proposed trial design needs a pilot study to demonstrate if recruitment is feasible.

We have run focus groups with older people who have IDA and received either oral or IV iron. They identified being symptom-free with improved quality of life and the ability to carry out daily tasks as the most desirable outcomes for therapy. They suggested that potential participants would be willing to receive an invitation letter to participate in the proposed study either from their own GP or their hospital consultant. They were uncertain about the idea of continuing oral iron if it had been ineffective, despite this being current standard practice. No ethical issues or concerns have been raised by clinicians or patients. However, we are aware of potential side effects of IV iron administration and therefore safety outcomes have been included as one of the secondary outcomes in this pilot.

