#### 7.1.3 Iron Infusion Visit

IV iron administration is a routine procedure in the NHS. Local policies and procedures will apply.

The infusion will be administered by a Registered Nurse / appropriately qualified member of the NHS team. The research team will remain blinded to treatment allocation.

The unblinded RN or delegate will attend the infusion visit.

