#### 7.2 SAFETY ASSESSMENTS

Adverse events will be collected at visit 2 and 4 by direct questioning of participants regarding health and social care contacts, hospitalisations and new symptoms. Details of current medication will be collected at visit 4. The participant's hospital medical record will be reviewed at visit 4; details of all AEs and concomitant medicines will be collected and recorded.

NOTE: Where a discrepancy is identified between participant and medical record reported AE / concomitant medication the PI, or medically trained delegate, will clarify and define the data to report; this decision will be recorded in the medical record.

AEs and concomitant medications are not collected at Visit 3 for the IV iron treatment group; the scientific justification for not collecting this data at Visit 3 is to prevent skewed/over- reporting due to additional data collection.

Where possible to investigators should remain blinded to treatment allocation.

The PI / medically qualified and delegated individual will be responsible for assessing severity and causality for any and all AEs and potential ADRs. Section 4.8 of the relevant SmPC will be used as reference safety information for the assessment of ARDs.

NOTE: SmPC will be as per locally used oral and IV iron preparations.

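### The care-seeking filter in section 10.1 under-ascertains the mild side effects that the synopsis makes a secondary outcome, and sections 2.2.2 and Table 3 omit that outcome

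*Protocol*

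**What the plan says.** **The outcome.** Item 6 of the secondary outcomes in S.2 is "reported side effects and adverse events (GI symptoms, headache, dizziness, rash", with the bracket closing there. Section 1.2, referring to the side effects of IV iron, states that "safety outcomes have been included as one of the secondary outcomes in this pilot". Section 9.2 plans a per-protocol analysis of completers aimed mainly at safety, and names adverse event rates. The eleven outcomes in section 2.2.2 and the entries in Table 3 include no side-effect or adverse event item.

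**What is recorded.** Section 10.1 sets the threshold: "Only AEs which have resulted in the participant seeking advice or treatment from a healthcare professional will be recorded". A later bullet in the same section has the investigator log an event on becoming aware of it, without repeating the threshold. Section 7.2 has staff question participants directly about care contacts, hospital stays and new symptoms. It adds a review of the hospital record at Visit 4.

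**When it is asked.** Section 10.1: "The PI or delegate will ask about the occurrence of AEs and hospitalisations visits 2 and 4 only". Section 7.2 adds that "AEs and concomitant medications are not collected at Visit 3 for the IV iron treatment group" and gives the reason, which "is to prevent skewed/over- reporting due to additional data collection". Section 7.1.4 places the Visit 4 adverse event questions after the blinded assessments.

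**The concern.** The four named symptoms are ones that many people put up with or manage themselves. A rule that records an event only when it led to professional contact measures the symptom and the decision to seek help together. For a pilot meant to inform a definitive trial of stopping, continuing or switching iron, that matters. Section 1.1 gives gastrointestinal side effects as one reason why oral iron fails, so tolerability is part of the case for comparing the strategies. A low recorded rate could be read as good tolerability when it partly reflects the recording rule.

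A second problem follows from the wording. A nurse told at Visit 4 about untreated nausea has been directed by 7.2 to ask about new symptoms, but is directed by 10.1 not to record this one. Sites could handle that differently. Because the outcome is missing from 2.2.2 and Table 3, it is also unclear whether it is a formal outcome.

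**Working it through.** The protocol gives no expected side-effect rate for this population and no care-seeking share, so there is no planned figure to reproduce. The check sets the data sources against the outcome and then shows how the bias scales.

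**Step 1. Which source yields a rate for each symptom?**

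| Source | GI | Headache | Rash | Dizziness |
|---|---|---|---|---|
| Adverse event log (10.1) | care-seeking only | care-seeking only | care-seeking only | care-seeking only |
| Symptom form (Appendix 1), baseline and monthly | no item | no item | no item | yes |
| Experience questionnaire (Appendix 4) | free text | free text | free text | free text |

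Appendix 4 is where section 9.2 says tolerability is assessed, and no filter applies to it. Its treatment questions are open-ended and go to thematic analysis, and its scored items concern the study rather than symptoms. For GI symptoms, headache and rash, the filtered log is therefore the only source of a rate.

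**Step 2. When are events asked about?** Visit 2 is the telephone call that tells participants their allocation (7.1.2, Table 4), so it comes before the allocated strategy starts. It is not a drug-free period, because everyone enters on oral iron. Visit 4 is the only later routine enquiry. Table 4 puts it at 3 months, plus or minus 3 weeks, with no stated anchor. Assume 13 weeks from randomisation:

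- Visit 4 falls between 13 − 3 = 10 and 13 + 3 = 16 weeks after randomisation.
- The infusion falls 0 to 2 weeks after randomisation, so the look-back to it is 10 − 2 = 8 to 16 − 0 = 16 weeks.

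**Step 3. How does the recorded rate relate to the true one?** Let p be the true proportion of an arm with a symptom, s the share of those who seek professional help, and r the share of those events retrieved at Visit 4 by questioning or record review. Then

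recorded rate = p × s × r.

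This is below p whenever s × r is below 1. Neither s nor r is in the protocol. With r = 1 and s as an assumption:

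| s | Recorded rate as a share of p |
|---|---|
| 0.75 | 75% |
| 0.50 | 50% |
| 0.25 | 25% |
| 0.10 | 10% |

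Imperfect recall lowers these further: s = 0.50 with r = 0.80 gives 0.50 × 0.80 = 40% of p.

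**Step 4. What happens to the between-arm difference?** Write k = s × r for each arm. The recorded difference is p₁k₁ − p₂k₂. If k is the same in both arms, the true difference shrinks by the factor k. If k differs, the difference can shrink, grow or change sign. With equal true rates p but k₁ = 0.50 and k₂ = 0.25 (assumed), a spurious difference of 0.50p − 0.25p = 0.25p appears. The trial is open-label and only one arm has an infusion visit with staff present, so equal k cannot be taken for granted.

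**The case against.** **This is a pilot.** The co-primary outcomes are recruitment rate and route. The study is a non-CTIMP, section 6.1 says it does not compare the safety or efficacy of the iron preparations, and no progression rule based on adverse events is stated. A threshold limits the logging burden in a population with much comorbidity. This stands, and it limits how serious the point is. It does not explain naming four mild symptoms as an outcome and then filtering them.

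**Tolerability is covered elsewhere.** Partly true. Appendix 4 goes to all participants, so the plan does look at tolerability, and Appendix 1 captures dizziness. Neither gives rates for the other three symptoms.

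Three stronger readings are tempting, and the protocol does not support them.

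- *Infusion reactions are lost because nothing is collected at Visit 3.* The recording period runs from consent to the last visit, and the investigator must log events on becoming aware of them. Section 12.6.1 has a nurse present throughout the infusion, and 7.1.3 adds that "The unblinded RN or delegate will attend the infusion visit". A reaction that was treated would arguably pass the care-seeking test, and the Visit 4 record review could recover it. The reason given for the Visit 3 rule, equal ascertainment across arms, is a legitimate one.
- *Section 10.1.1 contradicts 10.1.* It says "we will record all Adverse Events but not report to REC those classified as SAEs", but the sentence goes on to a list of categories, all of them deaths, hospitalisations or admissions. These are care contacts that 10.1 records anyway. The wording is loose but does not clearly conflict.
- *The side-effect figure of up to 40% in section 1.1 can be turned into a count of missed cases in the oral iron arm.* That is an upper figure for oral iron users in general. Entrants have already taken oral iron for at least 8 weeks, so people who could not tolerate it may already have stopped, and recording begins only at consent. The protocol gives no basis for an expected count.

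**Conclusion.** The point holds as under-ascertainment. If 10.1 is followed, the rates of GI symptoms, headache and rash, and of dizziness as an adverse event, will be too low in every arm. The direction is firm and needs only that some affected participants do not seek help or do not recall the event. The size is unknown: 25% to 75% of the true rate over the assumed care-seeking range of 0.25 to 0.75 with perfect recall, and less with imperfect recall. The direction of bias in a between-arm difference cannot be stated.

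Two text faults need no assumption. The outcome in S.2 and section 1.2 is absent from 2.2.2 and Table 3, and 7.2 asks about new symptoms that 10.1 may then exclude.

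It would go too far to say that the plan cannot measure side effects at all, or that treated infusion reactions will be missed. Mild, untreated infusion-day symptoms face the same filter and recall as any other mild symptom, but that loss cannot be quantified from the protocol. This should be fixed, and it does not threaten the main purpose of the pilot.

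**What to change.** 1. In section 10.1, exempt GI symptoms, headache, dizziness and rash from the care-seeking filter. Ask about each from a fixed yes/no checklist at Visit 4 in all three arms, over the same reference period. Do this after the blinded outcome assessments, where 7.1.4 already places adverse event collection, so the assessor's blinding is not put at risk before the outcomes are measured.
2. Reconcile 7.2 with 10.1, so that it is clear which new symptoms elicited by questioning are recorded.
3. Add the side-effect outcome of S.2 to section 2.2.2 and Table 3, with its timepoint.

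The cost is one short checklist on the Visit 4 CRF, wording changes in four places, and a few more minor events to log and code. Other adverse events can stay under the existing threshold.

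An infusion-day record is optional. The attending unblinded nurse could complete a separate quarantined form, tabulated apart from the between-arm comparison. This trades earlier capture against the protocol's stated wish to avoid extra collection in one arm, and the choice is the sponsor's.
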